Mammography is the process of using low-energy X-rays to examine the human breast, which is used as a diagnostic and screening tool. The goal of mammography is the early detection of breast cancer, typically through detection of characteristic masses and/or microcalcifications.

Magnetic Resonance Imaging(MRI)

MRI will be done at baseline and end of treatment to observe changes in pelvic floor muscles along with the thickness of the endometrium (mm). Quantitative assessments may include the area of the levator, the anteroposterior and transverse diameters, and/or other relevant parameters. Endometrial thickness can accurately be assessed by MRI (Stanislavsky, Weerakkody, et al., 2015; Nakamura et al., 2014); therefore, it is being used as a safety assessment in this study.

Medical, Epidemiological and Social Aspects of Aging (MESA) Questionnaire

The MESA questionnaire measures severity of specific types (stress, urgency, mixed) of urinary incontinence (UI). Two subscales, the urgency UI (6 items) and the stress UI (9 items). Test-retest reliability on “any incontinence” is high (agreement coefficient = .89). Validity (agreement between self-report on the MESA and clinician’s assessment) = 87% in women. The MESA questionnaire has demonstrated agreement on incontinence = 79% and 69% and 72% accuracy in predicting urodynamic diagnosis of stress UI and uninhibited detrusor contraction (Herzog, 1990a; Herzog, 1990b).

3 Day Voiding Diary

Subjects will record each episode of urinary leakage and record its severity. Subjects will also be asked to record urinary frequency, and urgency. Urine volume will also be recorded. 3 day bladder diaries are reliable measures of mean number of UI episodes/day, UI type, mean voids/24 hours, and mean voids during sleeping hours. 2-week test-retest results correlate with diurnal micturition ($r=.89$, $p<0.001$) and UI episodes ($r=.91$, $p<0.001$). Compared to participant recall of the previous week, Spearman rank correlation = .57 for voiding frequency and .70 for UI episodes (Brown, 2003; Locher, 2001; Wyman, 1988). For this study, any episode of vaginal discharge or spotting will also be recorded on the diary.

Patient Global Impression of Improvement (PGI-I)

PGI-I is a global rating of improvement using 7-point scale. Construct validity was established in two randomized controlled studies ($n=1,133$ subjects) of drug treatment for predominant stress incontinence (Wagner, 1996; Yalcin, 2003).

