Patient Global Impression of Severity (PGI-S)

PGI-S is a global rating of symptoms severity using a 7 point scale (Yalcin, 2003).

UDI-6 and IIQ-7

The Urogenital Distress Inventory (UDI-6) and Incontinence Impact Questionnaire (IIQ-7) assess symptom distress and the impact of urinary incontinence on daily life. The

urogenital distress inventory (UDI) and incontinence impact questionnaire (IIQ) were both developed to assess the impact of UI on HRQoL (Shumaker, 1994; Wyman, 1987). Short versions of the UDI and IIQ, UDI- 6, and IIQ-7, were developed to reduce the respondents' burden. The UDI-6 and IIQ-7 are both "A grade" recommended by the Fourth International Consultation on Incontinence (Shumaker, 1994; Wyman, 1987; Uebersax, 1995; Staskin, 2008).

Female Sexual Function Index (FSFI)

The FSFI is a 19-question validated tool evaluating sexual function in several domains: libido, arousal, lubrication, orgasm, satisfaction and pain (Rosen et al, 2000). Each subdomain is scored separately and the total score is calculated.

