- Change in Patient Global Impression of Severity (PGI-S) Scale from Baseline to Week 12 will be computed and this change will be summarized with descriptive statistics (min, max, median, mean, standard deviation) and analyzed for a significant change from Baseline using the Exact Wilcoxon sign rank test.
- Patient Global Impression of Improvement (PGI-I) Scale at Week 12. Descriptive statistics, (min, max, median, mean, standard deviation) will summarize these scores.
- Change in total score on the Urinary Distress Inventory (UDI-6) from Baseline to Week 12 will be computed and this change will be summarized with descriptive statistics (min, max, median, mean, standard deviation) and analyzed for a significant change from Baseline using the Exact Wilcoxon sign rank test.
- Change in total score on the Incontinence Impact Questionnaire (IIQ-7) from Baseline to Week 12 will be computed and this change will be summarized with descriptive statistics (min, max, median, mean, standard deviation) and analyzed for a significant change from Baseline using the Exact Wilcoxon sign rank test.
- Change in total score on the Female Sexual Function Index (FSFI) as well as the change in subdomain scores: libido, arousal, lubrication, orgasm, satisfaction, and pain from Baseline to Week 12 will be computed and these changes will be summarized with descriptive statistics (min, max, median, mean, standard deviation) and analyzed for a significant change from Baseline using the Exact Wilcoxon sign rank test.

- Changes in pelvic floor muscles from Baseline to Week 12 will be summarized with descriptive statistics (min, max, median, mean, standard deviation) and analyzed for a significant change from Baseline using the Exact Wilcoxon sign rank test.
- Qualitative changes in pelvic muscles will be described as decreased, increased or no change at Week 12 relative to Baseline.

Exploratory Analyses

Changes from baseline to each of the assessment times prior to Week 12 for the above endpoints will be explored, described and tested for significance using the same analytical methods noted for the primary and secondary objectives above. Durability treatment will be assessed by evaluating changes in study measures between week 12 and 16 (end of study). There will be no adjustment for multiple testing, nor will any data be imputed.

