2/27 = 7%	6/27 = 22%	10/27 = 37%	14/27 = 52%	18/27 = 67%	22/27 = 81%	26/27 = 96%
3/27 = 11%	7/27 = 26%	11/27 = 41%	15/27 = 56%	19/27 = 70%	23/27 = 85%	27/27 = 100%
4/27 = 15%	8/27 = 30%	12/27 = 44%	16/27 = 59%	20/27 = 74%	24/27 = 89%	

Total Score _____/27

2. APPENDIX B: PATIENT GLOBAL IMPRESSION OF SEVERITY (PGI-S) SCALE AND PATIENT GLOBAL IMPRESSION OF IMPROVEMENT (PGI-I) SCALE

Patient Global Impression of Severity (PGI-S) Scale

Check the one number that best describes how your urinary tract condition is now.

1. Normal
2. Mild
3. Moderate
4. Severe

Patient Global Impression of Improvement (PGI-I) Scale

Check the one number that best describes how your urinary tract condition is now, compared with how it was before you began taking medication in this study.

1. Very much better
2. Much better
3. A little better
4. No change
5. A little worse
6. Much worse
7. Very much worse

3. APPENDIX C: URINARY DISTRESS INVENTORY (UDI-6) AND INCONTINENCE IMPACT QUESTIONNAIRE (IIQ-7)

Urinary Distress Inventory (UDI-6)

1. Do you experience, and, if so, how much are you bothered by frequent urination?

Not at all **0** *Slightly* **1** *Moderately* **3** *Greatly***4**

2. Do you experience, and, if so, how much are you bothered by urine leakage related to the feeling of urgency?

Not at all **0** *Slightly* **1** *Moderately* **3** *Greatly***4**

3. Do you experience, and, if so, how much are you bothered by urine leakage related to physical activity, coughing, or sneezing?

Not at all **0** *Slightly* **1** *Moderately* **3** *Greatly***4**

4. Do you experience, and, if so, how much are you bothered by small amounts of urine leakage (drops)?

Not at all **0** *Slightly* **1** *Moderately* **3** *Greatly***4**

5. Do you experience, and, if so, how much are you bothered by difficulty emptying your bladder?

Not at all **0** *Slightly* **1** *Moderately* **3** *Greatly***4**

6. Do you experience, and, if so, how much are you bothered by pain or discomfort in the lower abdominal or genital area?

Not at all **0** *Slightly* **1** *Moderately* **3** *Greatly***4**

Incontinence Impact Questionnaire (IIQ-7)

7. Has urine leakage affected your ability to do household chores (cooking, cleaning, laundry, etc)?

Not at all **0** *Slightly* **1** *Moderately* **3** *Greatly***4**

8. Has urine leakage affected your physical recreation such as walking, swimming, or other exercise?

Not at all **0** *Slightly* **1** *Moderately* **3** *Greatly***4**

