9. Has urine leakage affected your entertainment activities (movies, concerts, etc.)?

Not at all **0** *Slightly* **1** *Moderately* **3** *Greatly***4**

10. Has urine leakage affected your ability to travel by car or bus more than 30 minutes from home?

Not at all **0** *Slightly* **1** *Moderately* **3** *Greatly***4**

11. Has urine leakage affected your participation in social activities outside your house?

Not at all **0** *Slightly* **1** *Moderately* **3** *Greatly***4**

12. Has urine leakage affected your emotional health (nervousness, depression, etc.)?

Not at all **0** *Slightly* **1** *Moderately* **3** *Greatly***4**

13. Has urine leakage affected your feeling frustrated?

Not at all **0** *Slightly* **1** *Moderately* **3** *Greatly***4**

14. Total Score for UDI-6= _____

15. Total Score for IIQ-7= _____

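### UDI-6 and IIQ-7 responses are coded 0, 1, 3, 4 with no stated reason, so totals formed from the printed codes give the Slightly/Moderately step double weight

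*Combined protocol and SAP*

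**What the plan says.** Appendix C holds one form with six UDI-6 items and seven IIQ-7 items. Each item offers four ordered responses. Not at all carries the code 0, and the other three are printed as "Slightly* 1 *Moderately* 3 *Greatly*4". The form ends with two blank lines, "Total Score for UDI-6" and "Total Score for IIQ-7", with no formula, range or recoding instruction.

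Section 8 describes both questionnaires and cites their sources but does not say how they are scored. Section 3.3 lists the change in each total as a secondary endpoint. Section 10.1 states, for the first, "Change in total score on the Urinary Distress Inventory (UDI-6) from Baseline to Week 12 will be computed", and for the second, "Change in total score on the Incontinence Impact Questionnaire (IIQ-7) from Baseline to Week 12 will be computed". Both changes are summarised descriptively and tested with the exact Wilcoxon signed-rank test.

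On a separate and smaller matter, Section 8 states that "PGI-S is a global rating of symptoms severity using a 7 point scale", whereas the PGI-S form in Appendix B has four levels, from Normal to Severe.

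**The concern.** Four ordered categories with codes 0, 1, 3, 4 are not evenly spaced, and nothing in the protocol says that the uneven spacing is intended. The pattern is the same on every item, so it is unlikely to come from reading the PDF.

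If totals are formed from these codes, a subject's change depends partly on where on the scale she starts as well as on how many steps she moves. The signed-rank test ranks the absolute size of the changes and attaches their signs, so the spacing feeds directly into the test statistic. It also affects the means and standard deviations reported beside it. Under Exploratory Analyses in Section 10.1, the same totals enter the changes before Week 12, the Week 12 to 16 durability comparison and the mixed-model slope, because Table 1 schedules these questionnaires at baseline and at Weeks 4, 8, 12 and 16.

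**Working it through.** **Inputs.** Printed codes 0, 1, 3, 4 (Appendix C); 6 items for UDI-6 and 7 for IIQ-7 (Appendix C); analysis of change in total score (Section 10.1). The comparator is equal-step coding 0, 1, 2, 3 of the same four categories. The plan states no range or maximum for either total, so there is no figure of its own to reproduce. I assume that the total is a sum of the printed codes.

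**Step sizes per item**

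| Move (either direction) | Printed codes | Equal steps | Share of item range, printed | Share, equal |
|---|---|---|---|---|
| Not at all / Slightly | 1 − 0 = 1 | 1 | 1/4 = 25% | 1/3 = 33.3% |
| Slightly / Moderately | 3 − 1 = 2 | 1 | 2/4 = 50% | 33.3% |
| Moderately / Greatly | 4 − 3 = 1 | 1 | 1/4 = 25% | 33.3% |

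Relative to the item range, the middle step counts (2/4)/(1/3) = 1.5 times its equal-step value, and each outer step counts (1/4)/(1/3) = 0.75 times.

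**Maxima**

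- UDI-6: 6 × 4 = 24 as printed, 6 × 3 = 18 with equal steps.
- IIQ-7: 7 × 4 = 28 as printed, 7 × 3 = 21 with equal steps.

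**Size of change, limiting case.** Suppose every item improves by one step. On UDI-6 that is 6 × 2 = 12 points if all items start at Moderately, but 6 × 1 = 6 points if all start at Greatly or all at Slightly. With equal steps it is 6 points from any of these starts. These are bounds and not a typical subject.

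**Rank.** Subject A moves one item from Moderately to Slightly. Subject B moves two items from Greatly to Moderately. As printed, both change by −2 and tie. With equal steps A changes by −1 and B by −2, so they are ranked apart.

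**Sign**

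- One item Moderately to Slightly and one item Moderately to Greatly: −2 + 1 = −1 as printed; −1 + 1 = 0 with equal steps.
- Two items Greatly to Moderately and one item Slightly to Moderately: −1 − 1 + 2 = 0 as printed; −1 − 1 + 1 = −1 with equal steps.

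The first subject is counted as improved only under the printed codes, the second only under equal steps.

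**Does the result depend on summing?** Only weakly. A mean of the item codes, or any linear rescaling of the total, multiplies every step by the same constant and keeps the 2:1 ratio. Only item-level recoding removes it.

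**PGI-S levels.** Section 8 says 7; the Appendix B form counts 4. For PGI-I, Section 8 says "PGI-I is a global rating of improvement using 7-point scale" and its form runs to "7. Very much worse", so that pair agrees. The PGI-S pair does not.

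**The case against.** **The documents cannot prove a misprint.** They cite the instruments but do not reproduce the published scoring. This stands. A reader might infer an error from the MESA form in Appendix A, whose maxima of 18 over 6 items and 27 over 9 items imply 3 per item and so suggest 0 to 3 coding. That inference is not safe. MESA is a different questionnaire and prints no item codes. Uneven codes also appear elsewhere in the appendices: the Appendix E diary scores leakage, urgency and pain as 0, 1, 5, 10 and discharge amount as 1, 2, 3, 5.

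**Section 10.1 does not say that the codes are summed.** This also stands. For the diary endpoints the section spells out the summation; here it says only total score. But the total lines sit on the form that carries the codes, no other scoring is offered, and the 2:1 ratio survives any linear use of them.

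**The double weight might be taken as a bias towards the drug.** The documents do not support that reading. Worsening from Slightly to Moderately also counts 2, so the effect is on size, rank and sometimes sign, with no built-in direction. Nor is the signed-rank test shown to be invalid.

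**The stakes are limited.** Two of the twelve secondary endpoints in Section 3.3 are affected, in a single-arm study without a power calculation. That limits the weight of the point but does not remove it, since both endpoints are formally tested.

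**The PGI-S mismatch might be read as affecting an analysis.** It does not: the data follow the four-level form, and no planned calculation uses the number of levels.

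**Conclusion.** The point holds in a limited form. Appendix C prints unevenly spaced codes on all 13 items, and the plan supplies neither a reason nor an alternative scoring. If totals are built from those codes by a sum, mean or linear rescaling, one of the three adjacent steps carries twice the weight of the others, the maxima are 24 and 28 rather than 18 and 21, and a subject's change can differ in size, rank and occasionally sign from equal-step scoring. How often the sign differs, or the test result changes, depends on the distribution of responses, which the documents do not give.

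The conclusion rests on the printed codes being used for the totals. It does not rest on their being a misprint, which remains open. The primary endpoint is unaffected. The PGI-S discrepancy is a minor editorial note.

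**What to change.** 1. Check the Appendix C codes against the scoring of the validated instruments that Section 8 cites.
2. Unless the skipped 2 is confirmed as intended and justified in the protocol, either correct Appendix C or pre-specify in Section 10.1 that the ticked categories are recoded to 0, 1, 2, 3 before totals are computed.
3. In either case, state the total-score formula and resulting range for UDI-6 and IIQ-7 in Section 10.1.
4. As an editorial correction, reconcile the number of PGI-S levels in Section 8 with the form in Appendix B.

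The cost is a form correction or one recoding step at analysis. The answers are ticked verbal categories, so data already collected stay usable.

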4. APPENDIX D: FEMALE SEXUAL FUNCTION INDEX (FSFI)

Female Sexual Function Index (FSFI)

Name _____ Date _____

INSTRUCTIONS: These questions ask about your sexual feelings and responses during the past 4 weeks. Please answer the following questions as honestly and clearly as possible. Your responses will be kept completely confidential. In answering these questions the following definitions apply:

- Sexual activity can include caressing, foreplay, masturbation and vaginal intercourse.
- Sexual intercourse is defined as penile penetration (entry) of the vagina.
- Sexual stimulation includes situations like foreplay with a partner, self-stimulation (masturbation), or sexual fantasy.

CHECK ONLY ONE BOX PER QUESTION.

Sexual desire or interest is a feeling that includes wanting to have a sexual experience, feeling receptive to a partner's sexual initiation, and thinking or fantasizing about having sex.

1. Over the past 4 weeks, how **often** did you feel sexual desire or interest?

- Almost always or always
- Most times (more than half the time)
- Sometimes (about half the time)
- A few times (less than half the time)
- Almost never or never

2. Over the past 4 weeks, how would you rate your **level** (degree) of sexual desire or interest?

- Very high
- High
- Moderate
- Low

Very low or none at all

Sexual arousal is a feeling that includes both physical and mental aspects of sexual excitement. It may include feelings of warmth or tingling in the genitals, lubrication (wetness), or muscle contractions.

3. Over the past 4 weeks, how **often** did you feel sexually aroused ("turned on") during sexual activity or intercourse?

- No sexual activity
- Almost always or always
- Most times (more than half the time)
- Sometimes (about half the time)
- A few times (less than half the time)
- Almost never or never

4. Over the past 4 weeks, how would you rate your **level** of sexual arousal ("turn on") during sexual activity or intercourse?

- No sexual activity
- Very high
- High
- Moderate
- Low
- Very low or none at all

5. Over the past 4 weeks, how **confident** were you about becoming sexually aroused during sexual activity or intercourse?

- No sexual activity
- Very high confidence
- High confidence
- Moderate confidence
- Low confidence
- Very low or no confidence

6. Over the past 4 weeks, how **often** have you been satisfied with your arousal (excitement) during sexual activity or intercourse?

- No sexual activity
- Almost always or always

- Most times (more than half the time)
- Sometimes (about half the time)
- A few times (less than half the time)
- Almost never or never

7. Over the past 4 weeks, how **often** did you become lubricated ("wet") during sexual activity or intercourse?

- No sexual activity
- Almost always or always
- Most times (more than half the time)
- Sometimes (about half the time)
- A few times (less than half the time)
- Almost never or never

8. Over the past 4 weeks, how **difficult** was it to become lubricated ("wet") during sexual activity or intercourse?

- No sexual activity
- Extremely difficult or impossible
- Very difficult
- Difficult
- Slightly difficult
- Not difficult

9. Over the past 4 weeks, how often did you **maintain** your lubrication ("wetness") until completion of sexual activity or intercourse?

- No sexual activity
- Almost always or always
- Most times (more than half the time)
- Sometimes (about half the time)
- A few times (less than half the time)
- Almost never or never

10. Over the past 4 weeks, how **difficult** was it to maintain your lubrication ("wetness") until completion of sexual activity or intercourse?

- No sexual activity
- Extremely difficult or impossible

- Very difficult
- Difficult
- Slightly difficult
- Not difficult

11. Over the past 4 weeks, when you had sexual stimulation or intercourse, how **often** did you reach orgasm (climax)?

- No sexual activity
- Almost always or always
- Most times (more than half the time)
- Sometimes (about half the time)
- A few times (less than half the time)
- Almost never or never

12. Over the past 4 weeks, when you had sexual stimulation or intercourse, how **difficult** was it for you to reach orgasm (climax)?

- No sexual activity
- Extremely difficult or impossible
- Very difficult
- Difficult
- Slightly difficult
- Not difficult

13. Over the past 4 weeks, how **satisfied** were you with your ability to reach orgasm (climax) during sexual activity or intercourse?

- No sexual activity
- Very satisfied
- Moderately satisfied
- About equally satisfied and dissatisfied
- Moderately dissatisfied
- Very dissatisfied

14. Over the past 4 weeks, how **satisfied** have you been with the amount of emotional closeness during sexual activity between you and your partner?

- No sexual activity

- Very satisfied
- Moderately satisfied
- About equally satisfied and dissatisfied
- Moderately dissatisfied
- Very dissatisfied

15. Over the past 4 weeks, how **satisfied** have you been with your sexual relationship with your partner?

- Very satisfied
- Moderately satisfied
- About equally satisfied and dissatisfied
- Moderately dissatisfied
- Very dissatisfied

16. Over the past 4 weeks, how **satisfied** have you been with your overall sexual life?

- Very satisfied
- Moderately satisfied
- About equally satisfied and dissatisfied
- Moderately dissatisfied
- Very dissatisfied

17. Over the past 4 weeks, how **often** did you experience discomfort or pain during vaginal penetration?

- Did not attempt intercourse
- Almost always or always
- Most times (more than half the time)
- Sometimes (about half the time)
- A few times (less than half the time)
- Almost never or never

18. Over the past 4 weeks, how **often** did you experience discomfort or pain following vaginal penetration?

- Did not attempt intercourse
- Almost always or always
- Most times (more than half the time)

- Sometimes (about half the time)
- A few times (less than half the time)
- Almost never or never

19. Over the past 4 weeks, how would you rate your **level** (degree) of discomfort or pain during or following vaginal penetration?

- Did not attempt intercourse
- Very high
- High
- Moderate
- Low
- Very low or none at all

Thank you for completing this questionnaire

Protocol: GTx-024 as a Treatment for Stress Urinary Incontinence in Women: A Proof of Concept Study

Compound No.: GTx-024
 Author: _____

5. APPENDIX E: VOIDING DIARY

VOIDING DIARY

Wake Time: _____

Study ID: _____

Bed Time: _____

Date (m/d/y): _____

Time	Fluid Intake (ounces)	Urine Amount cc's/ml's or ounces (oz)	Leaking (if you leak, first give the episode a "score" in the first column then circle if you think it is stress or urge incontinence, or both in the second column)		Urgency	Pad Replaced	Bowel Movement	Pelvic and/or Bladder/Urinary Related Pain	Vaginal discharge color	Vaginal discharge amount
A: a.m. P: p.m.		Amount Voided	0: None 1: Mild 5: Mod. 10: Severe	S: Stress U: Urge	0: None 1: Mild 5: Mod. 10: Severe	1: Tissue 2: Pantiliner 3: Thick Pad 4: Diaper	N: Normal C: Constipated D: Diarrhea L: Leaking stool	0: None 1: Mild 5: Mod 10: Severe	0: no discharge 1: red 2: brown 3: white 4: yellow	1: Spotting 2: dime size 3: quarter size 5: more than quarter size
5:00 AM				S U						
A P				S U						
A P				S U						
A P				S U						
A P				S U						
A P				S U						
A P				S U						
A P				S U						
A P				S U						
A P				S U						
A P				S U						
A P				S U						
A P				S U						
A P				S U						
A P				S U						
A P				S U						
A P				S U						
A P				S U
